3.1.1 Number of Patients

Approximately 100 patients are expected to be enrolled in this study, at approximately 50 investigative sites in Europe and North America. Of those who are enrolled, at least 20 patients who are < 18 years of age will be treated with study drug, and at least 40 patients across all tumor type cohorts will be treated and available for response assessment (at least two tumor type cohorts must enroll a minimum of 10 patients).

Accrual is expected to last approximately 3 years.

3.1.2 Enrollment Stopping Rules

Enrollment in a tumor type cohort may be stopped if any one of the following criteria is met:

- The number of patients needed for initial response assessment is reached and the number of responders does not meet the requirement for additional tumor type cohort expansion.

- The number of patients needed for additional response assessment is reached.
- The Sponsor has stopped the study.
- *At least two tumor type cohorts have enrolled the minimum number of patients needed for initial response assessment.*

Some exceptions may apply to these general stopping rules, including but not limited to the following:

- Enrollment in the study *may* be stopped if enrollment has been open for more than 2 years and at least 20 patients have been treated with the study.
- Enrollment in a tumor type cohort may be extended if there is strong evidence of a positive efficacy signal in a slow-enrolling and rare tumor type cohort, thus allowing for additional data to be collected.

3.1.3 Adverse Events Requiring Drug Discontinuation

Events that require study drug discontinuation reflect the known and expected toxicities of the mechanism of action of atezolizumab, in addition to accounting for serious unexpected adverse events that may occur. The following events require discontinuation of study drug if they occur at any time while undergoing treatment and are considered by the investigator to be related to atezolizumab (see [Table 1](#) for causality assessment). For situations of unclear attribution to study drug, investigators are encouraged to perform additional tests to determine the underlying etiology and most appropriate attribution.

Any one of the following events will require study drug discontinuation if they are assessed by the investigator to be related to atezolizumab:

- Grade ≥ 4 neutropenia (ANC $< 0.5 \times 10^9/L$) that lasts > 7 days
- Grade ≥ 4 neutropenia with documented infection
- Grade ≥ 3 febrile neutropenia that lasts > 5 days
- Grade ≥ 4 thrombocytopenia that lasts > 48 hours or any thrombocytopenia requiring a platelet transfusion, with the following exception:
 - For patients who have undergone autologous hematopoietic stem cell transplantation or ^{131}I -MIBG (metaiodobenzoguanine) therapy, Grade ≥ 4 thrombocytopenia that lasts > 7 days or any thrombocytopenia that requires a platelet transfusion on two or more separate dates will require study drug discontinuation.
- Grade ≥ 3 thrombocytopenia with a Grade ≥ 2 bleeding *event*
- Elevation of serum hepatic transaminase levels (ALT or AST) $\geq 5 \times$ the upper limit of normal (ULN)

For patients with elevated hepatic transaminase levels at baseline as a result of liver metastases, hepatic transaminase $\geq 5 \times$ baseline and $< 10 \times$ baseline

for >3 days, or any hepatic transaminase $\geq 10 \times$ baseline will require study drug discontinuation.

- Elevation of serum bilirubin level $\geq 3 \times$ ULN
- Grade ≥ 3 non-hematologic, non-hepatic adverse event, with the following exceptions:

Grade 3 fevers will not mandate study drug discontinuation.

Grade 3 mucositis or stomatitis that resolves to Grade ≤ 2 within 3 days will not mandate study drug discontinuation.

Grade ≥ 3 nausea or vomiting that responds to standard-of-care therapy within 3 days will not mandate study drug discontinuation. *In the ATRT cohort, this may mandate study drug discontinuation if Grade ≥ 3 nausea and/or vomiting is subsequent to increased intracranial pressure (see Section 4.5.3.1 for management guidelines).*

Grade 3 fatigue that lasts for ≤ 3 days will not mandate study drug discontinuation.

Grade 3 laboratory test abnormalities that are asymptomatic and considered by the investigator not to be clinically significant will not mandate study drug discontinuation.

Patients with Grade 3 rash may continue treatment with atezolizumab according to guidelines outlined in the Atezolizumab Investigator's Brochure.

- Conditions (regardless of grade) suggestive of an autoimmune disorder, including but not limited to rheumatoid arthritis, Type I diabetes, vasculitis, neuritis, and neuropathies including myasthenia gravis, Guillain-Barré syndrome, systemic lupus erythematosus, Sjögren's syndrome, and multiple sclerosis.

The following conditions may continue treatment with atezolizumab according to the guidelines outlined in Section 5.1.1 and the Atezolizumab Investigator's Brochure:

Hepatitis (elevation of transaminases), rash, pancreatitis (elevated amylase/lipase), pneumonitis/pulmonary toxicity, endocrinopathies, colitis (presence of diarrhea), eye toxicities, and systemic immune activation

- Pericardial effusion (any grade) if not attributable to disease
- Any toxicity that requires interruption of atezolizumab treatment for >105 days (*e.g., no more than 105 days between infusions*), except in patients who must be tapered off corticosteroids used to treat adverse events (see Section 5.1.1.1 for details). Longer periods of treatment interruption may be considered after discussion with the Medical Monitor.

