5.2.2 Serious Adverse Events (Immediately Reportable to the Sponsor)

A serious adverse event is any adverse event that meets any of the following criteria:

- Is fatal (i.e., the adverse event actually causes or leads to death)
- Is life threatening (i.e., the adverse event, in the view of the investigator, places the patient at immediate risk of death)

This does not include any adverse event that, had it occurred in a more severe form or was allowed to continue, might have caused death.

- Requires or prolongs inpatient hospitalization (see Section 5.3.5.11)
- Results in persistent or significant disability/incapacity (i.e., the adverse event results in substantial disruption of the patient's ability to conduct normal life functions)
- Is a congenital anomaly and/or birth defect in a neonate or infant born to a mother exposed to study drug
- Is a significant medical event in the investigator's judgment (e.g., may jeopardize the patient or may require medical or surgical intervention to prevent one of the outcomes listed above)

The terms "severe" and "serious" are not synonymous. Severity refers to the intensity of an adverse event (e.g., rated as mild, moderate, or severe, or according to NCI CTCAE v4.0 criteria; see Section 5.3.3); the event itself may be of relatively minor medical significance (such as severe headache without any further findings).

Severity and seriousness need to be independently assessed for each adverse event recorded on the eCRF.

Serious adverse events are required to be reported by the investigator to the Sponsor immediately (i.e., no more than 24 hours after learning of the event; see Section 5.4.2 for reporting instructions).

5.2.3 **Adverse Events of Special Interest (Immediately Reportable to the Sponsor)**

Adverse events of special interest, regardless of seriousness, are required to be reported by the investigator to the Sponsor immediately (i.e., no more than 24 hours after learning of the event; see Section 5.4.2 for reporting instructions). Adverse events of special interest for this study include the following:

- Pneumonitis
- Colitis
- Endocrinopathies
 - Diabetes mellitus
 - Pancreatitis
 - Adrenal insufficiency
 - Hyperthyroidism
 - Hypothyroidism
- Hepatitis
- Transaminitis Grade ≥ 2 (AST or ALT $> 3 \times$ ULN and bilirubin $> 2 \times$ ULN) or AST/ALT $> 10 \times$ ULN
- Systemic lupus erythematosus
- Neurological
 - Guillain-Barré syndrome
 - Myasthenia gravis
 - Meningoencephalitis
- Nephritis

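### Section 3.1.3 gives related Type I diabetes two consequences (must stop; may continue as an endocrinopathy) and does not say which stop items its may-continue list overrides

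*Combined protocol and SAP*

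**What the plan says.** Section 3.1.3 (Adverse Events Requiring Drug Discontinuation) sets the force of its list in one sentence: "Any one of the following events will require study drug discontinuation if they are assessed by the investigator to be related to atezolizumab". Three items matter here.

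- Transaminases: "Elevation of serum hepatic transaminase levels (ALT or AST") at or above 5 x ULN. The only qualification is a baseline-multiple rule for patients whose levels are raised at baseline because of liver metastases.
- Non-hematologic, non-hepatic events of Grade 3 or higher, with a list of exceptions. Rash is one of them: "Patients with Grade 3 rash may continue treatment with atezolizumab according to guidelines outlined in the Atezolizumab Investigator"'s Brochure. Colitis and pneumonitis are not among them.
- Autoimmune conditions: "Conditions (regardless of grade) suggestive of an autoimmune disorder, including but not limited to rheumatoid arthritis, Type I diabetes", followed by further named disorders.

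Directly under the autoimmune item, and before the next one (pericardial effusion), comes a permission: "The following conditions may continue treatment with atezolizumab according to the guidelines outlined in Section 5.1.1" and the Investigator's Brochure. The conditions are "Hepatitis (elevation of transaminases), rash, pancreatitis (elevated amylase/lipase), pneumonitis/pulmonary toxicity, endocrinopathies, colitis (presence of diarrhea), eye toxicities, and systemic immune activation". No grade, multiple of ULN or exclusion is attached to any of them.

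Section 5.2.3, the list of adverse events of special interest, puts "Diabetes mellitus" under the heading of endocrinopathies.

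**The concern.** A mandatory stop rule has to give one answer for each event it names. Here an investigator who attributes new Type I diabetes to the drug finds it named as a stop at any grade. The same investigator then finds, under the same item, that a class which the protocol elsewhere treats as containing diabetes may continue. The permission is also written without saying which of the stop items it qualifies.

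Two things are at stake. The first is patient safety, in a trial whose background (Section 1.2.2.1) says that no pediatric safety information has been established. The second is the analysis. Section 6.3 plans summaries of adverse events leading to treatment discontinuation and of treatment exposure, and both depend on how the rule is read.

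**Working it through.** No sample size, error rate or event count is involved, and the plan has no figure to reproduce. The check sets the passages side by side under the two possible scopes of the may-continue list.

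| Related event | Stop item | May-continue entry | List confined to the autoimmune item | List applies to the whole section |
|---|---|---|---|---|
| Type I diabetes, any grade | Autoimmune item, by name | Endocrinopathies | Both consequences | Both consequences |
| Hepatitis with ALT/AST at or above 5 x ULN | Transaminase item | Hepatitis | Stop | Both consequences |
| Colitis, Grade 3 or higher | Grade 3 or higher item | Colitis | Stop | Both consequences |
| Pneumonitis, Grade 3 or higher | Grade 3 or higher item | Pneumonitis | Stop | Both consequences |

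**Diabetes.** Both statements sit within the autoimmune item, so narrowing the scope of the permission does not separate them. The conflict disappears only if a named condition is taken to prevail over a general class. Section 3.1.3 states no such rule.

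**Hepatitis, colitis and pneumonitis.** Any single stop item is sufficient for discontinuation, so being excused under one does not excuse a patient under another. Two features of the text favor the narrow scope. The permission is placed under the autoimmune item. Also, rash appears on the may-continue list and has its own exception inside the Grade 3 or higher item, which would be redundant if the list already overrode that item. On this reading these conditions escape the any-grade autoimmune stop but remain subject to the 5 x ULN and Grade 3 or higher items. The text does not say so.

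**Other sections that might settle it.**

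- Section 5.1.1.2 covers only systemic immune activation in detail. It refers hepatic, endocrine, pulmonary and gastrointestinal events to the Brochure. It adds a permanent stop for life-threatening immune-mediated events and as the Brochure directs.
- Section 5.1.1 says the management guidelines do not replace clinical judgment.
- Section 4.1.2 admits patients with controlled Type 1 diabetes, but that concerns disease present at entry, not an on-treatment event attributed to the drug.

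**Exposure to the ambiguity.** Section 3.1.1 plans about 100 patients at about 50 sites: 100 / 50 = about 2 patients per site. Each site would apply the rule rarely. The documents give no pediatric rate for these events, so no number of affected patients can be derived.

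**The case against.** The strongest reply on diabetes is that Section 3.1.3 names Type I diabetes as a stop, while endocrinopathies is a general term under a permissive verb; an ordinary reader would let the named item control. Section 5.2.3 is also a list for 24-hour reporting, not a definition for stopping. Its grouping does not match Section 3.1.3: it puts pancreatitis under endocrinopathies, whereas Section 3.1.3 lists the two separately. This stands in part, because Section 5.2.3 is imperfect support. But the precedence remains unwritten, and it is the only classification of diabetes as an adverse event that the protocol offers.

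A reader might infer that transaminases at or above 5 x ULN, or severe colitis and pneumonitis, also carry directly opposite instructions. The documents do not support that. On the narrow scope, which the placement and the separate rash exception favor, the stop items govern and there is no contradiction. What remains is an unstated scope.

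A reader might also infer that discontinuation will differ between sites. The documents show only that it could. The rule turns on investigator attribution, and the Brochure, which is not among the documents, may give clear guidance. Even then, the protocol does not say whether that guidance overrides a stop at any grade. Diabetes, hepatitis, colitis and pneumonitis are all reportable to the sponsor within 24 hours, so cases would be visible centrally. That tempers the worry about unnoticed variation but does not repair the wording.

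**Conclusion.** The point holds in two parts of unequal strength. The Type I diabetes conflict is in the current text, lies inside a single stop item, and is resolved by nothing in the protocol. The scope of the may-continue list is an ambiguity: harmless to the transaminase and Grade 3 or higher items on the better-supported reading, and in conflict with them on the other.

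The size is one named event with two consequences on either scope, plus three conditions whose handling depends on the scope. The number of patients affected cannot be estimated. The conclusion assumes that diabetes counts as an endocrinopathy, as Section 5.2.3 has it, and that no precedence rule exists in the protocol outside the sections checked. It takes no view on which clinical rule is right. Because the passage is a mandatory safety rule and feeds a planned safety summary, it should be corrected.

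**What to change.** Reconcile the stop items and the may-continue list in Section 3.1.3 with each other and with the grouping in Section 5.2.3, so that Type I diabetes appears under one consequence. Add a sentence saying which mandatory-stop items the may-continue list overrides and which it does not, naming the transaminase item and the Grade 3 or higher item. State whether the Brochure or Section 3.1.3 prevails where they differ. The clinical team must choose the rule.

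The cost is wording in one section, carried through an amendment, with no change to the sample size, assessments or analyses. Section 3.1.3 can be corrected at the same time where it cites Table 1 for causality: Table 1 is the severity scale, and the causality guidance is in Table 2.

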3.1.4 Independent Data Monitoring Committee

An iDMC will be set up to evaluate safety data during the study. The iDMC will evaluate study safety data on a periodic basis, approximately every 6 months from the point of first patient in (FPI). They will also have a scheduled review following enrollment of the

first 5 patients (mandated to be ≥ 2 years old). After this review, they will make recommendations on the appropriateness of enrolling patients who are < 2 years old. Members of the iDMC will be external to the Sponsor and the Investigator and will follow a charter that outlines their roles and responsibilities. Following their review, the iDMC will provide a recommendation as to whether the study may continue, whether amendment(s) to the protocol should be implemented, or whether the study should be stopped. The IDMC may also contribute to the selection of tumor types to be included in the cohort expansion. Specific details, such as committee composition, communication plan, and member roles and responsibilities, will be detailed in an iDMC Charter.

3.2 END OF STUDY

The end of this study is defined as the date when the last patient last visit (LPLV) occurs or 5 years after the last patient is enrolled, whichever occurs first. The Sponsor reserves the right to present interim data to health authorities for compliance purposes.

For an individual patient, the completion of the study (i.e., the last visit) will occur when the patient withdraws consent, has been lost to follow-up, or dies or when the study is stopped.

The primary analysis will be conducted after the enrollment has been completed and all enrolled patients have been followed up for at least 6 months. A Clinical Study Report will be submitted to health authorities.

3.3 RATIONALE FOR STUDY DESIGN

3.3.1 Rationale for Atezolizumab Starting Dose and Dose Modification

The pharmacokinetics of atezolizumab in the pediatric population are expected to be similar to those in adults on the basis of the observation of linear pharmacokinetics, suggestive of nonspecific elimination, in the clinically relevant dose range. Therefore, a pediatric dosing scheme for atezolizumab that provides reliable and adequate exposure for maximal efficacy while minimizing the potential for adverse events may be predictable from PK data in adults, provided that effects of body size are well characterized.

Few studies in the literature have investigated developmental changes in absorption, distribution, and elimination of therapeutic proteins. Tissue distribution of therapeutic proteins occurs primarily through transvascular transport processes such as convection and diffusion, which are not expected to be significantly affected by differences in body composition as a function of age ([Anderson and Lynn 2009](#); [Tabrizi et al. 2010](#); [Xu et al. 2013](#)). The distribution of a therapeutic protein may be influenced by binding to plasma proteins or tissue targets; however, differences in antigen production or degradation rates may not be sufficient to alter the distribution of an antibody-based therapeutic protein that exceeds a 100-fold molar ratio relative to the targeted antigen

(Xu et al. 2013). Therefore, clinically meaningful differences in monoclonal antibody distribution are not expected between adult and pediatric patients after taking into account differences in body size. Monoclonal antibodies are metabolized by the same catabolic pathways as endogenous proteins and are eliminated by nonspecific Fc receptor–mediated catabolism and/or target-mediated disposition (Tabrizi et al. 2006; Mould and Green 2010). For atezolizumab, the nonspecific elimination pathway appears to be primary, as evidenced by linear pharmacokinetics in the dose range of 1–20 mg/kg, which includes the *approved dose (for treatment of adult patients with urothelial carcinoma) and recommended Phase II/III dose currently under investigation in multiple cancer types (1200 mg; equivalent to a weight-based dose of 15 mg/kg assuming an adult body weight of 80 kg)*. Because infants and children are able to maintain homeostasis of immunoglobulins, it is presumed that they are able to break down therapeutic monoclonal antibodies if Fc receptor–mediated catabolism is the major pathway. Thus, no age-related developmental differences in disposition are expected for therapeutic proteins with nonspecific elimination as the major pathway. A primary elimination pathway for atezolizumab via Fc receptor–mediated catabolism suggests that the pharmacokinetics of monoclonal antibodies in pediatric patients can be predicted from adult data, particularly in children who are >6 years of age (Xu et al. 2013).

Of the potential covariates that may affect the pharmacokinetics of antibody-based therapeutic proteins, body size (weight or body surface area) is the most frequently identified and clinically relevant covariate (Dirks and Meibohm 2010). A review of the PK characteristics of 12 approved therapeutic proteins showed comparable steady-state peak and trough concentrations and terminal half-life between pediatric and adult patients after adjustment for body size (Xu et al. 2013). Age alone does not appear to affect the clearance of monoclonal antibodies (Dirks and Meibohm 2010; Xu et al. 2013). Because the total clearance of antibody-based therapeutic proteins does not increase in proportion to increasing body weight, a 2-fold increase in body weight usually results in a less than 2-fold increase in clearance (Bai et al. 2012; Xu et al. 2013). Therefore, the lightest pediatric patients who received the same body weight–based dose level of atezolizumab may have a lower drug exposure than adults. Furthermore, because the development of ATAs has been associated with changes in pharmacokinetics for some adult patients in the lower-dose cohorts of Study PCD4989g (i.e., 0.3, 1, and 3 mg/kg), the possibility for lower exposure may be exacerbated, particularly in the lightest children. Children aged <18 years will receive the weight-based equivalent of the *approved adult dose and recommended Phase II/III adult dose (15 mg/kg atezolizumab every 3 weeks, with a maximum of 1200 mg)*. Patients who are ≥18 years old will receive *the approved adult dose of 1200 mg*. Dose adjustments may be made, if necessary, to achieve exposures corresponding to those measured in adult patients and if the safety profile is acceptable.

Dose levels for modification will be determined on the basis of the available information regarding PK exposure, interim PK analyses, and the emerging safety profile.

3.3.2 Rationale for Inclusion of Patients Aged >18 Years

The Sponsor expects that the majority of enrolled patients will be < 18 years old. However, there may be young adult patients with “pediatric-type” tumors who are treated in pediatric oncology facilities. In a specific analysis of adolescent and young adult patients in the United States, limited clinical trial participation correlated with the relative lack of improvement in survival prolongation and cancer death rates (Bleyer et al. 2006). The lower participation of adolescent and young adult patients in clinical trials has created significant knowledge gaps with respect to cancer biology, treatment, and other factors affecting the survival of adolescent and young adult patients with cancer. As part of the Sponsor’s commitment to the development of personalized medicine, adolescent and young adult patients up to the age of 30 years (and in exceptional cases of relapsed pediatric tumors, beyond 30 years) will be included in this study.

